11.3.1 Intensity and Causality Assessments

Where appropriate, the Investigator must assess the intensity (severity) of the AE based on medical judgment with consideration of any subjective symptom(s), as defined below:

Intensity (Severity)

Mild An AE is mild if the subject is aware of but can easily tolerate the sign or

symptom.

Moderate An AE is moderate if the sign or symptom results in discomfort significant

enough to cause interference with the subject's usual activities.

Severe An AE is severe if the sign or symptom is incapacitating and results in the

subject's inability to work or engage in their usual activities.

For every AE in the study, the Investigator must assess the causality (Related or Not Related to the medical device or study procedure). An assessment of causality will also be performed by Study Sponsor utilizing the same definitions, as shown below:

Causality

Related An AE classified as related may be either definitely related or possibly related

where a direct cause and effect relationship with the medical device or study procedure has not been demonstrated, but there is a reasonable possibility that

the AE was caused by the medical device or study procedure.

Not Related An AE classified as not related may either be definitely unrelated or simply

unlikely to be related (ie, there are other more likely causes for the AE).

Document: TDOC-0056258 Version: 3.0; Most-Recent; Effective; CURRENT

Status: Effective Page 42 of 57

The Study Sponsor will assess the AEs and may upgrade the Investigator's assessment of seriousness and/or causality. The Study Sponsor will notify the Investigator of any AEs that is upgraded from non-serious to serious or from unrelated to related.

11.4 Return Product Analysis

Study Sponsor representatives and their contact information are provided in the MOP that accompanies this protocol.

Alcon products associated with device deficiencies and/or product related AEs should be returned and must include the Complaint #, which will be provided by Study Sponsor after the case is entered in the Study Sponsor's Global Product Complain Management System (GPCMS).

11.5 Unmasking of the Study Information

Not applicable; this study is an unmasked, observational, single-arm study.

11.6 Follow-up of Subjects with Adverse Events

The Investigator is responsible for adequate and safe medical care of subjects during the study and for ensuring that appropriate medical care and relevant follow-up procedures are maintained after the study.

The Investigator should provide the Study Sponsor with any new safety information (which includes new AEs and changes to previously reported AEs) that may affect the safety evaluation of the device. For AEs that are unresolved/ongoing at time of subject exit from study, any additional information received at follow-up should be documented in the eCRFs up to study completion (ie, database lock).

All complaints received after this time period will be considered and processed as spontaneous (following the postmarket vigilance procedures) and should be communicated to the medical device's manufacturer as per local requirements.

11.7 Pregnancy in the Clinical Study

Pregnancy is not reportable as an AE; however, complications may be reportable and will be decided on a case-by-case basis. An Alcon form will be utilized to capture all pregnancy-related information until birth of the child.

Document: TDOC-0056258 Version: 3.0; Most-Recent; Effective; CURRENT

Status: Effective Page 43 of 57

12 ANALYSIS PLAN

12.1 Subject Evaluability

Final subject evaluability must be determined prior to locking the database, based upon the Deviations and Evaluability Plan.

12.2 Analysis Sets

12.2.1 Enrolled

The analysis set for both the safety and effectiveness analyses will be the set of all enrolled subjects. Only subjects enrolled in this study will be summarized.

12.3 Demographic and Baseline Characteristics

Demographic characteristics will be summarized overall. Counts and percentages will be presented for categorical variables such as sex, age and race. Baseline ECD will be summarized overall. Study eye will be tabulated.

12.4 Safety Analyses

The primary objective of the study is to assess long-term (10 years post-CyPass implantation) status of the corneal endothelium in subjects who were implanted with the CyPass Micro-Stent in the COMPASS trial.

The safety endpoints are:

- Rate of occurrence of sight-threatening adverse events (AEs)
- Rate of occurrence of ocular AEs
- Central and peripheral (nasal) ECD measurements
- Analyses of rate of loss and rate of low ECD (ie, $\leq 1000 \text{ cells/mm}^2$)
- Assessment of stabilization of ECL
- Corneal sequelae associated with ECL
- Association between peripheral and central ECD count and number of observed rings
- Secondary surgical interventions (SSIs) to modify the device position (eg, repositioning, trimming, explanation)
- Effects of SSIs on central and peripheral ECD
- CyPass Micro-Stent movement and/or malposition

Document: TDOC-0056258 Version: 3.0; Most-Recent; Effective; CURRENT

Status: Effective Page 44 of 57

Corneal AEs (eg, corneal decompensation, tube corneal touch, corneal edema, etc.)
 caused by CyPass Micro-Stent

- Losses in Best Corrected Visual Acuity (BCVA) ≥10 letters
- Change in visual field mean deviation (MD)
- Change in central corneal thickness

There are no safety hypotheses planned in this study. The focus of the safety analysis will be to assess the long-term status of the corneal endothelium and a comprehensive descriptive assessment of occurrence of adverse events as well as the other listed parameters.

All adverse events reported to Alcon will be accounted for in the reporting. Since some of the data collection for this study will be retrospective, some of the adverse events will have occurred prior to the date of informed consent. Descriptive summaries (counts and percentages) and listings will be presented.

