	Gonioscopy (with goniophotography)
	Ultrasound biomicroscopy (UBM)/Optical coherence tomography (OCT; if available at the site)
	Slit-lamp examination
	Visual field

Document: TDOC-0056258 Version: 3.0; Most-Recent; Effective; CURRENT

Status: Effective Page 18 of 57

Status: Effective	Page 18 01 57
Study Design	 Fundus examination with C:D ratio Specular microscopy (central and peripheral [nasal] endothelial cell density) Ocular adverse events (these include but are not limited to corneal haze/edema, device malposition, device explantation, device trimming, device repositioning) occurring since exit visit from COMPASS or COMPASS XT (whichever was the last study visit) will be captured as ocular history Prospective; non-interventional, non-randomized; unmasked; observational; single-arm; total duration of subject's participation in the study is follow-up visits scheduled annually and an exit visit.
	in the study is follow-up visits scheduled annually and an exit visit when the subject has reached 10 years post-CyPass implantation; duration of study is up to 4 years. For some subjects, the first visit will be at or after 10 years post-CyPass implantation, and therefore the first visit may coincide with the 120-Month/Exit visit.
	Because collection of ECD is not part of standard of care, retrospective data collection will not be attempted for visits that occurred prior to subject enrollment. The one exception will be ocular adverse events data, which will be collected for all visits, wherever available.
Subject population	Subjects who were implanted with a CyPass Micro-Stent in the COMPASS trial. Planned number of subjects enrolled/consented: Up to 374 (total number implanted with a CyPass Micro-Stent in the COMPASS trial) Planned number of completed subjects: Up to 374
Key inclusion criteria	Any subject who was implanted with a CyPass Micro-Stent as a participant in the COMPASS trial.

Document: TDOC-0056258 Version: 3.0; Most-Recent; Effective; CURRENT

Status: Effective Page 19 of 57

Associated materials	N/A
Key words	Prospective; non-interventional, observational, multi-center study; being conducted in the US only; up to 374 enrolled and up to 374 complete annual follow-up visits; 10 years post-CyPass implantation

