11.2 Monitoring of Ocular Adverse Events

At each visit, the Investigator should inquire about any ocular AEs occurring since the last study visit.

- "Have you had any health problems since your last study visit?"
- "Have there been any changes in the medicines you take since your last study visit?"

Document: TDOC-0056258 Version: 3.0; Most-Recent; Effective; CURRENT

Status: Effective Page 40 of 57

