11.3 Procedures for Recording and Reporting

Any ocular AEs occurring since the Exit visit from the COMPASS trial or the COMPASS XT trial (whichever was the last study visit) will be collected from the time of informed consent. Any pre-existing medical conditions or signs/symptoms present in the subject in the COMPASS trial or COMPASS XT trial are not considered AEs in the study and should be recorded in the Medical History section of the eCRF. However, a worsening of the pre-existing ocular AEs are considered AEs.

For each recorded event, the ADEs and SAEs documentation must include: date of occurrence, severity, treatment (if applicable), outcome, and assessments of the seriousness and causality. In addition, the Investigator must document all device deficiencies reported or observed with test and control articles on the Device Deficiency eCRF. The site must submit all available information on ADEs, SAEs, and device deficiencies to the Study Sponsor immediately as follows:

- All SAEs must be reported immediately (within 24 hours) of the Investigator's or site's awareness.
- ADEs that do not meet seriousness criteria and device deficiencies must be reported within 10 calendar days of the Investigator's or site's awareness.

A printed copy of the completed *Serious Adverse Event and Adverse Device Effect* and/or *Device Deficiency* eCRF must be included with product returns.

- Additional relevant information after initial reporting must be entered into the eCRF as soon as the data become available.
- Document any changes to concomitant medications on the appropriate eCRFs.
- Document all relevant information from Discharge Summary, Autopsy Report,
 Certificate of Death etc., if applicable, in narrative section of the Serious Adverse
 Event and Adverse Device Effect eCRF.

Note: Should the EDC system become non-operational, the site must complete the appropriate paper Serious Adverse Event and Adverse Device Effect and/or Device Deficiency Form. The completed form is emailed to the Study Sponsor at [contact] according to the timelines outlined above; however, the reported information must be entered into the EDC system once it becomes operational.

Document: TDOC-0056258 Version: 3.0; Most-Recent; Effective; CURRENT

Status: Effective Page 41 of 57

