12.4.2.2 Analysis Methods

Descriptive statistics for ocular adverse events (including SSIs) will be presented for study eyes. The rates of all adverse events will be provided with counts and percentages, and these rates will be accompanied by two-sided exact 95% confidence intervals. An eye with multiple

Document: TDOC-0056258 Version: 3.0; Most-Recent; Effective; CURRENT

Status: Effective Page 45 of 57

ocular adverse events of the same preferred term is only counted once toward the total of this preferred term.

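### Ocular AE percentages merge retrospectively gathered events with events found at scheduled COMPASS XXT examinations; a split by onset period is needed to read them.

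*Protocol*

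**What the plan says.** Protocol 11.3 starts the AE look-back at the previous study's exit: "Any ocular AEs occurring since the Exit visit from the COMPASS trial or the COMPASS XT trial", whichever came last. For that interval the Protocol Summary (Section 3) says that "retrospective data collection will not be attempted for visits that occurred prior to subject enrollment", and then: "The one exception will be ocular adverse events data, which will be collected for all visits, wherever available". SAP 1.2 repeats both statements. Protocol 11.2 adds open questions at each visit, such as "Have you had any health problems since your last study visit"; at the first XXT visit that question reaches back several years.

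From entry onward, Table 3-1 schedules annual ETDRS acuity, visual field, gonioscopy with ring count, slit-lamp and fundus examination with C:D ratio until month 120.

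The analysis does not separate the two periods. Protocol 12.4 and SAP 4.3.15 acknowledge that "some of the adverse events will have occurred prior to the date of informed consent". Protocol 12.4.2.2 then states: "The rates of all adverse events will be provided with counts and percentages", with exact 95% intervals. Sections 12.4.1.2 (sight-threatening events) and 12.4.10.2 (stent movement or malposition) do the same, as do SAP 4.3.1.2, 4.3.2.2 and 4.3.10.2. The set is all enrolled subjects (12.2.1: "Only subjects enrolled in this study will be summarized"). No section uses eye-time for AEs.

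One passage pulls the other way. The assessment list in Protocol Section 3 says that AEs since the last exit, "whichever was the last study visit) will be captured as ocular history".

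**The concern.** A percentage with an exact binomial interval invites the reader to take it as the cumulative risk, with sampling error as the only uncertainty. Here it also depends on how completely events before consent were captured, and the interval says nothing about that. A low figure could mean few events or poor capture.

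Timing is a separate difficulty. Several anticipated AEs in Protocol 11.1.1 are defined by measurements: 10-letter acuity loss (a), C:D increase of 0.3 (s), confirmed MD worsening of 2.5 dB (t) and a ring change of at least 1 (dd). XXT schedules none of these before consent. Unless routine care recorded them, they come to light at the first XXT visit. A cluster there could look like late onset when it only marks the start of scheduled examination. The stent-movement rate (12.4.10) and the BCVA-loss listing (12.4.12, which uses AE data as its source) are both exposed to this.

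**Working it through.** The documents give no figure for the AE observation periods, so there is none to reproduce. The 374 is a cap equal to all CyPass implants and is not based on power. The calendar is consistent: 75 + 430 = 505 randomized, and March 2013 plus 120 months plus 120 days is about July 2023, just before the August 2023 date in Table 7-1.

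**Inputs from the documents**
- Implantation: September 2009 to August 2010 (75 of 505) and July 2011 to March 2013 (430 of 505), from Protocol 5.1.
- Last prior exit: month 24 for COMPASS; month 60 for COMPASS XT, not before XT opened in April 2016 (5.1).
- XT share: 215/374 = 57.5% (12.8).
- Exit from XXT at month 120 (7.1).

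**Assumptions**
- Implantation uniform within each phase, with the 75:430 split applying to CyPass eyes.
- Sites open in May 2020. The row labels of Table 7-1 were unreadable in the text used.
- Consent uniform over 6 months, 14 months (May 2020 to June 2021) or 39 months (to August 2023).

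The 6-month window is close to the planning rates in 7.6. At 4 new sites per month (24 at most) and 4 subjects per site per month, accrual is 16 + 32 + 48 + 64 + 80 + 96 = 336 after six months and passes 374 in the seventh. Because 7.6 also allows enrolment until the study ends, 39 months serves as an outer bound.

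**Formulas**, for implantation month t and consent month c:
- Last exit x = t + 24 (COMPASS only), or the later of t + 60 and April 2016 (XT).
- Retrospective time R = c − x.
- Examined time E = max(0, t + 120 − c).
- Share before consent = mean R / (mean R + mean E).

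Single eyes with consent in May 2020 (R / E, months):

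| Implanted | XT | COMPASS only |
|---|---|---|
| Sept 2009 | 49 / 0 | 104 / 0 |
| July 2011 | 46 / 14 | 82 / 14 |
| Nov 2012 | 30 / 30 | 66 / 30 |
| March 2013 | 26 / 34 | 62 / 34 |

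Simulated averages:

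| Consent window | Mean R, XT / COMPASS only | Mean E | Share before consent, XT / COMPASS only | Eyes with E = 0 |
|---|---|---|---|---|
| 6 months | 40.5 / 78.4 | 18.3 | 69% / 81% | 13% |
| 14 months | 44.5 / 82.4 | 14.9 | 75% / 85% | 14% |
| 39 months | 57.0 / 94.9 | 7.0 | 89% / 93% | 46% |

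For example, 40.5/(40.5 + 18.3) = 69% and 82.4/(82.4 + 14.9) = 85%. If everyone consented in May 2020, the range would be 64-78%.

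**Sensitivity to capture, illustration only.** Take the 14-month window at the 57.5% XT share. Mean R is 0.575 × 44.5 + 0.425 × 82.4 = 60.6 months (5.05 years), and E is 1.24 years. Assume a transient event with a hazard of 2% per year, fully detected after entry, with capture fraction s before consent. The pooled percentage is 1 − exp(−0.02 × (5.05s + 1.24)). That is 11.8% at s = 1, 9.6% at 0.75, 7.3% at 0.5 and 4.9% at 0.25. Neither the hazard nor s is in the documents, so this shows only that the result depends on s.

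**The case against.** The strongest reply is that the first XXT visit recovers much of what matters. Acuity loss is judged against the best COMPASS or XT value and MD worsening against the prior exit. Both, like ring and C:D changes, will be found at entry if they last, whenever they arose. Such events are mistimed, not missed. Persistent 3-line loss is by definition judged at study exit, and gap surgery is asked for under ocular surgical history (10.2.4). This stands: a reader might infer that the pooled rate understates the measurement-defined AEs, and the documents do not support that for lasting changes.

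A reader might also infer that the time before consent went unexamined. The documents say only that XXT schedules nothing then and that AE data come from whatever is available. Routine visits may have been well recorded, some at the same sites. At full capture there is no understatement.

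The plan also discloses the retrospective events and promises listings. The SSI listing carries dates, the BCVA listing carries acuity data from all three studies, and ring counts and MD are shown by visit. That helps with individual cases but does not qualify the percentages.

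Finally, it is tempting to make post-entry events the headline. With the same denominator, that percentage can never exceed the pooled one, and it would discard gap events and first-visit findings. It should not replace the pooled figure.

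**Conclusion.** The point holds as one of interpretability. One percentage per term mixes two modes of ascertainment, and about 69-85% of the time it covers precedes consent for consent windows of 6 to 14 months (89-93% as an outer bound). This rests on May 2020 opening, uniform accrual within phases, and XT shares from 100% to 0%. It is an average: XT eyes implanted after about November 2012 and entering in May 2020 have more examined than retrospective time.

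Understatement is possible mainly for transient, resolved or undocumented events, and the documents do not allow its size to be estimated. For lasting measurement-defined changes the risk is misdating. The study is descriptive and its objective is the corneal endothelium, so this is a worthwhile, inexpensive improvement to the AE reporting and leaves the primary objective untouched.

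**What to change.** In Protocol 12.4.1.2, 12.4.2.2 and 12.4.10.2, and SAP 4.3.1.2, 4.3.2.2, 4.3.10.2 and 4.3.15:

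1. Keep the pooled row as the cumulative figure since the last study exit. State that it is a lower bound because capture before consent depends on available records.
2. Add three rows per term, classifying each eye by its first occurrence so that the rows sum to the pooled count: (a) onset before consent; (b) first detected at the first XXT visit, with no earlier documented onset; (c) onset after the first XXT visit. Give eye-years for (a) and (c).
3. Use (c) only for statements about the yearly rate under scheduled examination.
4. Confirm that onset date is recorded for every ocular AE. Protocol 11.3 expressly requires date of occurrence only for ADEs and SAEs. Row (b) may also need a detection field or a derivation rule.
5. Reconcile the ocular-history wording in Protocol Section 3 with 11.3 and 12.4. If look-back events were held only as history, they would drop out of the AE percentages and row (a) would be empty.

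The cost is SAP wording, extra table rows and a check of the AE form; no visit or examination is added. Row (c) has fewer eye-years and a wider interval, and about 13-14% of eyes (up to about 46% with late enrolment) contribute no time to it. The split shows where the evidence comes from; it does not recover missed events.

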12.4.1 Rate of Occurrence of Sight-Threatening Adverse Events (AEs)

12.4.1.1 Statistical Hypotheses

No hypothesis testing of the endpoint is planned.

12.4.1.2 Analysis Methods

Descriptive statistics for sight-threatening adverse events will be presented for study eyes. The rates of all sight-threatening adverse events will be provided with counts and percentages, and these rates will be accompanied by two-sided exact 95% confidence intervals. An eye with multiple ocular adverse events of the same preferred term is only counted once toward the total of this preferred term. The list of adverse events which are considered to be sight-threatening can be found in Section 11.1.2.

12.4.2 Rate of Occurrence of Ocular AEs

12.4.2.1 Statistical Hypotheses

No hypothesis testing of the endpoint is planned.

12.4.2.2 Analysis Methods

Descriptive statistics for ocular adverse events (including SSIs) will be presented for study eyes. The rates of all adverse events will be provided with counts and percentages, and these rates will be accompanied by two-sided exact 95% confidence intervals. An eye with multiple

Document: TDOC-0056258 Version: 3.0; Most-Recent; Effective; CURRENT

Status: Effective Page 45 of 57

ocular adverse events of the same preferred term is only counted once toward the total of this preferred term.

12.4.3 Central and Peripheral (Nasal) ECD Measurements

12.4.3.1 Statistical Hypotheses

No hypothesis testing of the endpoint is planned.

12.4.3.2 Analysis Methods

Central and peripheral (nasal) endothelial cell density will be summarized at each visit. The number of eyes, mean, standard deviation, and the following percentiles will be reported: 0th, 5th, 25th, 75th, 95th, and 100th. A 95% confidence interval based on the t-distribution will be reported for the mean at each visit.

The central endothelial cell coefficient of variation and hexagonality will be summarized by visit, in separate tables. The number of eyes, mean, standard deviation, and the following percentiles will be reported: 0th, 5th, 25th, 75th, 95th, and 100th.

12.4.4 Analyses of Rate of Loss and Rate of Low ECD (ie, ≤ 1000 cells/mm²)

12.4.4.1 Statistical Hypotheses

No hypothesis testing of the endpoint is planned.

12.4.4.2 Analysis Methods

Change in central endothelial cell density (within-eye) from baseline and percent change in central endothelial cell density will be summarized by visit. Baseline central endothelial cell density is the data collected at the COMPASS Study baseline visit. All references to baseline endothelial cell density data throughout this protocol refer to data from this visit. The proportion of subjects with central endothelial cell density less than 1000 cells/mm², the proportion of subjects with peripheral endothelial cell density less than 1000 cells/mm², the proportion of subjects with central endothelial cell density less than 500 cells/mm², and the proportion of subjects with central endothelial cell density less than 500 cells/mm², and the proportion of subjects with central endothelial cell loss over 30% from baseline will also be reported at these time points. A 95% exact binomial confidence interval will be presented for the proportions. The following statistics will be presented for change in central endothelial cell density at each visit: number of eyes, means, standard deviations, and the following percentiles: 0th, 5th, 25th, 75th,

Document: TDOC-0056258 Version: 3.0; Most-Recent; Effective; CURRENT

Status: Effective Page 46 of 57

95th, and 100th. A 95% confidence interval based on the t-distribution will be reported for the means at each visit. This analysis will be performed using central endothelial cell density data from visits in the COMPASS, COMPASS XT, and COMPASS XXT studies, where available, and using peripheral cell density data collected in this study. Summary statistics for peripheral (nasal) endothelial cell density will be presented for each study visit.

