11.1.1 Postoperative Adverse Events

Anticipated postoperative AEs include, but are not limited to, the following complications.

Document: TDOC-0056258 Version: 3.0; Most-Recent; Effective; CURRENT

Status: Effective Page 36 of 57

a) BCDVA loss of 2 lines (10 letters) or more on the ETDRS chart in comparison with the best BCDVA reported in COMPASS/COMPASS XT

- b) Persistent (at time of study exit) BCDVA loss of 3 or more lines compared to best BCDVA achieved during the course of study, including both the COMPASS trial, and the COMPASS XT trial
- c) 2-point worsening to severe on the slit-lamp examination findings (other than cells and flare) not associated with a pre-existing condition
- d) Endophthalmitis
- e) Flat AC with lens cornea touch
- f) Shallow AC with iridocorneal apposition
- g) Shallow AC with peripheral iridocorneal apposition
- h) Aqueous misdirection
- i) Chronic iritis
- j) Conjunctivitis
- k) Keratitis
- 1) Corneal edema
- m) Corneal opacification
- n) Corneal decompensation
- o) Hyphema (defined as persistent hyphema of ≥ 2 mm)
- p) Vitreous hemorrhage
- q) Retinal detachment
- r) Other retinal complications (eg, dialysis, flap tears, or proliferative vitreoretinopathy)
- s) Increase in C:D ratio of ≥ 0.3 units on slit-lamp biomicroscopic examination
- t) Confirmed worsening in the visual field mean deviation (MD) of \geq 2.5 dB compared to the MD determined at the exit of the COMPASS trial or the COMPASS XT trial

Document: TDOC-0056258 Version: 3.0; Most-Recent; Effective; CURRENT

Status: Effective Page 37 of 57

 Choroidal hemorrhage or choroidal effusion, defined as a choroidal effusion or detachment with at least a partially hemorrhagic component that obstructs vision or causes pain (including both peripheral and "kissing" choroidal detachments) lasting longer than 1 month

- v) Peripheral anterior choroidal effusion
- w) Maculopathy associated with hypotony
- x) Maculopathy associated with cystoid edema
- y) Hypotony (defined as IOP < 6 mmHg)
- z) Clinically significant hypotony, defined as IOP < 6 mmHg with any of the following findings:
 - i. Maculopathy
 - ii. Flat AC chamber requiring reformation
 - iii. Corneal folds
 - iv. Worsening of with-the-rule astigmatism by ≥ 1 diopter, or rotation of against-the-rule astigmatism to ≥ 1 diopter of with-the-rule astigmatism
 - v. Choroidal effusion requiring surgical drainage
 - vi. Suprachoroidal hemorrhage
 - vii. BCDVA loss of ≥ 2 lines from the best postoperative BCDVA

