11.1.2 Sight Threatening Adverse Events

Of the postoperative AEs listed in Section 11.1.1, the following are pre-defined as sight threatening and must therefore be reported as SAEs per the guidelines for reporting in Section 11.3:

Document: TDOC-0056258 Version: 3.0; Most-Recent; Effective; CURRENT

Status: Effective Page 39 of 57

• Persistent (at time of study exit) BCDVA loss of 3 or more lines compared to best BCDVA achieved during the course of study

- Endophthalmitis
- Corneal decompensation
- Retinal detachment
- Severe choroidal hemorrhage or detachment
- Aqueous misdirection

Other AEs may also be considered potentially sight threatening, or may meet other seriousness criteria. Any AE meeting any SAE seriousness criterion, as defined in the Glossary of Terms, must be reported as an SAE per Section 11.3.

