12.4.5.2 Analysis Methods

The annualized rate of change and percent rate of change in central endothelial cell density will be summarized at each year of observation. A 95% confidence interval based on the t-distribution will be produced along with the mean, standard deviation, minimum, median and maximum. This analysis will be performed using central endothelial cell density data from visits in the COMPASS, COMPASS XT, and COMPASS XXT studies, where available.

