12.4.6.2 Analysis Methods

A listing of corneal sequelae associated with ECL will be provided.

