12.4.11.2 Analysis Methods

A listing of corneal AEs caused by the CyPass Micro-Stent will be provided, which will include central and peripheral ECD measurements, where available.

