12.7 Handling of Missing Data

Missing data imputation will not be performed.

Document: TDOC-0056258 Version: 3.0; Most-Recent; Effective; CURRENT

Status: Effective Page 52 of 57

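### The low-ECD, cell-loss and annualized-rate analyses have no visible rule for eyes that cannot be counted because the cornea failed, or for readings taken after endothelial replacement

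*Protocol*

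**What the plan says.** The single objective is the status of the corneal endothelium 10 years after implantation (Protocol 6.1; SAP 1.1).

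- **Low ECD and loss.** Protocol 12.4.4.2 and SAP 4.3.4.2 summarize "The proportion of subjects with central endothelial cell density less than 1000" cells/mm², further proportions at 1000 and 500, and the proportion with central loss over 30% from the COMPASS baseline, each with an exact binomial 95% confidence interval. The source is described thus: "This analysis will be performed using central endothelial cell density data from visits in the COMPASS, COMPASS XT, and COMPASS XXT studies, where available".
- **Stabilization.** Protocol 12.4.5.2 and SAP 4.3.5.2: "The annualized rate of change and percent rate of change in central endothelial cell density will be summarized at each year of observation", again from available data in the three studies.
- **Missing data.** Protocol 12.7 and SAP 6: "Missing data imputation will not be performed". No distinction is made by reason.
- **Denominator.** The analysis set is all enrolled subjects (Protocol 12.2.1). No denominator is stated for the ECD proportions, although one is stated for visual field (Protocol 12.4.13.2).
- **Corneal failure.** "Corneal decompensation" is an anticipated event in Protocol 11.1.1, beside corneal edema and opacification. It is also on the list in 11.1.2, of which the Protocol says "the following are pre-defined as sight threatening and must therefore be reported as SAEs". Its rate is reported under 12.4.1.2. Protocol 12.4.6.2 adds: "A listing of corneal sequelae associated with ECL will be provided". The listing of device-caused corneal events in 12.4.11.2 is one "which will include central and peripheral ECD measurements, where available".

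Neither document mentions endothelial replacement.

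**The concern.** Whether a reading exists can depend on the quantity being measured. An endothelium that has failed badly enough may yield no cell count, and the Protocol allows for this when it lists ECD in eyes with corneal events only where a value exists. Such an eye should bear on the low-ECD and loss rates, but nothing in the visible text brings it in. After endothelial replacement the reading describes donor tissue, yet nothing visible stops it being compared with the COMPASS baseline as if it were native.

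At stake are the low-ECD proportion, the proportion with loss over 30%, and the annualized rate on which the stabilization endpoint rests. The exact interval reflects sampling error only and would not reveal the problem.

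**Working it through.** **Inputs.** The plan states no expected low-ECD, failure or replacement rate and makes no power or precision claim, so there is no figure to reproduce. From the documents: 374 implanted and 215 enrolled in COMPASS XT (Protocol 12.8), and the exact binomial interval (12.4.4.2). Assumed: N = 215 eyes due at a visit, 6 readable low eyes, k failed eyes, and a fraction q of those k that are truly low.

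**1. Readable-eye denominator.** With p = 6/(N − k), reported minus true = (k/N)(p − q). The reported rate is too low only if q > p.

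| k | q | Reported (exact 95% CI) | True | Difference, points |
|---|---|---|---|---|
| 0 | – | 6/215 = 2.79% (1.03–5.97) | 2.79% | 0 |
| 1 | 1 | 6/214 = 2.80% (1.04–6.00) | 7/215 = 3.26% | −0.45 |
| 2 | 1 | 6/213 = 2.82% (1.04–6.03) | 8/215 = 3.72% | −0.90 |
| 5 | 1 | 6/210 = 2.86% (1.06–6.11) | 11/215 = 5.12% | −2.26 |
| 5 | 0.5 | 6/210 = 2.86% | 8.5/215 = 3.95% | −1.10 |
| 5 | 0 | 6/210 = 2.86% | 6/215 = 2.79% | +0.07 |

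**2. All-enrolled denominator.** The failed eye stays in and counts as not low. For k = 5, q = 1: 6/215 = 2.79% against 5.12%, or −2.33 points. The same figure results if five replaced eyes each give a reading at or above the threshold. So under either denominator a failed eye is not counted as low.

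**3. Sensitivity to the assumptions (k = 5, q = 1, readable-eye denominator).**
- Relative understatement at N = 215: 1 − (6/210)/(11/215) = 44%. With 11 readable low eyes, 1 − (11/210)/(16/215) = 30%. With 20, 1 − (20/210)/(25/215) = 18%.
- N = 374: 6/369 = 1.63% (0.60–3.51) against 11/374 = 2.94%.
- N = 150: 6/145 = 4.14% (1.53–8.79) against 11/150 = 7.33%.

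In each of these the true rate lies inside the reported interval. That is not a general law: with N = 374, 7 readable low and 11 failed eyes, 7/363 = 1.93% (0.78–3.93) excludes 18/374 = 4.81%.

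**4. Annualized rate.** Assume one eye reads 500 to 1500 cells/mm² higher after replacement, among 215 paired readings. Relative to no change in that eye, the mean moves by 500/215 = +2.3 to 1500/215 = +7.0 cells/mm² per year over a one-year interval. COMPASS XT ran to month 60 (Protocol 5.1) and the first visit scheduled here is month 84 (Table 3-1). Across that gap of at least two years the shift is at most half: +1.2 to +3.5.

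**The case against.** The strongest reply is that corneal failure is already reported. Decompensation has a rate and exact interval, ocular events including secondary surgery have theirs, and corneal sequelae and device-caused corneal events are listed. The number of eyes is given for ECD at each visit. The annualized rate comes with median and maximum, so one large gain would show as the maximum while the median barely moved. The study is descriptive, with no hypothesis or decision threshold. This limits the harm, but none of these outputs feeds the low-ECD proportion or the rate of loss, and no visible table shows how many eyes lack a reading because the cornea failed.

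A reader might go further and infer that the plan discards failed eyes and classes replaced eyes as healthy, so that its low-ECD rate must be too low. The documents do not support that:

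- The handling is inferred from silence. The reference to available data may chiefly say which visits of three studies contribute, and the denominator is unstated.
- A replaced eye is not low only if its reading reaches the threshold.
- Readability or evaluability rules may sit in the Manual of Procedures, the Deviations and Evaluability Plan, or sections absent from the public text (Protocol 12.4.15 and 12.5; SAP 4.3.16.2, 4.6, 5 and 8). None of these was seen.
- Every magnitude is assumed. The 44% figure requires that 5 of 11 low eyes failed and that every failed eye was low.

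**Conclusion.** The concern holds as a gap in the visible text. The ECD proportions and the annualized rate rest on available readings without imputation, and no rule covers failed or replaced endothelium. The low-ECD and loss rates are understated if such eyes occur and are low more often than readable eyes. If none occur there is no bias, and if failed eyes are low less often the rate is slightly too high.

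With 215 eyes, 6 readable low eyes and one to five failed eyes all low, the understatement is about 0.45 to 2.3 points, inside the planned interval. The shift towards stabilization from one replaced eye is a few cells/mm² per year at most, given 215 pairs; fewer pairs would make it larger. These are illustrations, not estimates. A change is worth making because it is cheap and bears on the sole objective, not because a large bias has been shown.

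**What to change.** Amend Protocol 12.4.4.2 and 12.4.5.2 and SAP 4.3.4.2 and 4.3.5.2. If a rule already exists in a document not seen here, cite it in the SAP instead.

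- **(a)** Exclude readings after endothelial replacement from native-ECD means, change, annualized rate and counts of eyes that are not low. Report the number excluded.
- **(b)** Keep the observed-only proportion. State its denominator as eyes with a reading at that visit (and at baseline, for loss over 30%). Report eyes without a reading by reason: corneal failure or opacity, replacement, other.
- **(c)** Add one supportive sensitivity proportion per visit, labelled a composite and not imputation. It counts as low, and as loss over 30%, any eye with recorded corneal decompensation or endothelial replacement by that visit. A decompensated eye with a valid native reading at that visit keeps its reading. The denominator is eyes with a native reading at that visit plus the eyes so counted. Base it on the recorded event: causality is recorded against device or procedure (Protocol 11.3.1), not cell loss, so requiring that attribution would add an unmasked judgement not now collected. List the eyes counted.

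**Cost.** An amendment to a design that follows an FDA agreement, one derived flag from adverse-event and surgical-history data already collected, and a few table rows. The second rate may be less favourable and may include failures from other causes.

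**Separate minor consistency corrections.** The endpoint is at or below 1000 (Protocol Table 6-1 and 12.4; SAP 4.1), but the analyses use below 1000 (Protocol 12.4.4.2 and 12.4.16; SAP 4.3.4.2 and 4.7); align them to the endpoint. Protocol 12.4.4.2 repeats central density below 500 where the SAP has peripheral; use the SAP's.
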